b.Justification: The increase in oropharyngeal space created by advancing the mandible with OAs has shown efficacy in reducing the number of apnea events, comparable AHI reduction results with CPAP ⁸ and improvements in secondary health benefits. ^{5,6,8} Furthermore, several studies provide evidence that OA compliance is greater among OSA patients using OA therapy compared with CPAP use. ²⁰

- 1.Principle of Operation: Midline Traction Oral Appliance ¹¹ (Figure 1) A coupling mechanism located at a single point midline, allows adjustment by incremental protraction of the mandible by the patient, see Hoekema⁷.
- 2.Principle of Operation: Bilateral Thrust Oral Appliance ¹² (Figure 2) A bilateral torsion adjustment mechanism constructed from surgical grade stainless steel allows for the mandible to be pushed forward. The patient can modify the amount of protrusion by adjusting the mechanism on each of the two sides, but this cannot be done while in the mouth.

c.Investigative question

Does the MT or BT device provide greater RDI reduction to an acceptable level (<10 apnea and hypopnea events/hour of recorded sleep or >50% change) from pretreatment values in adult patients with moderate to severe OSA?

III.Theoretical framework

The UA consists of the nasopharynx, oropharynx and hypopharynx. The oropharynx is essentially a tube of tissue derived from embryonic pharyngeal arches. Its patency is maintained by the tensor veli palatini and the genioglossus muscles. The oropharynx is that part of the pharynx (throat) posterior to the oral cavity. Its volume is constrained by the size and position of the tongue, the soft palate, uvula, tonsils, and pharyngeal muscles relative to the hard-tissue framework formed by the teeth, maxillary complex, mandible and hyoid bone. The genioglossus muscle originates at the superior genial tubercle of the mandible and fans into the substance of the tongue (intrinsic tongue muscles). The geniohyoid muscle originates at the inferior genial tubercle and inserts into the hyoid bone.

During normal breathing, swallowing and phonation, detectable physiological changes occur within the oropharynx. During wake in an upright position, the normal breathing position of the mandible is at 'rest' in a plane parallel to the maxillary plane. 23

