b. Population

- 1. Adults (n=44) with moderate to severe OSA.
- 2. Potential study participants will be recruited by means of flyers posted at the College of Dentistry, Dallas A.W.A.K.E. office (support group for sleep apnea patients) and Dallas area sleep clinics. Online postings at clinicaltrials.gov and the College web site. Also post flyers at (1) regional hospitals and clinics, (2) city and county offices/stations (such as the Dallas Fire Department), (3) DART and other transportation offices and (4) Facebook, Twitter and similar site, (5) local newspapers and magazines, (6) local radio stations. The content of the advertisements on venues (5) and (6) will be the same as the approved flyers. Written permission will be sought from all sites at which flyers are to be posted. Data analyst and subjects will be blinded to treatment device type (i. e. sequence of use of the two OAs) and subject's identity will be coded.
- 3. Controls and Controlling Confounders: Subjects serve as their own controls; their baseline polysomnography (PSG) or Home Sleep Test (HST), untreated values (from full or split night PSGs) will serve as their control values for evaluating treatment effects with each of the two OAs. The focus of the trial is on comparing OA appliance efficacy in reducing the RDI (AHI); the presentation, fitting, monitoring and adjustment of the two OAs will be the same for both arms of the study. For the operators, there will be concealed allocation of assignment of subjects to treatment.
- 4. Performance Site: Texas A&M College of Dentistry, [name]. Seventh floor room 725, two operatory clinic.

c. Inclusion criteria

OSA diagnosed adults, at least 18 years old, who have been recently diagnosed by polysomnography (PSG) or polygraphy home sleep test (HST) in the previous year and are currently being treated with continuous positive airway pressure (CPAP) having an AHI > 15 events/hour of sleep; two or more OSA symptoms (snoring, witnessed apnea or daytime hypersomnolence complaint); at least 8 teeth per arch to support either OA device; Mallampati score from I to III; Palatine tonsils – grade 0, 1, or 2; Central and mixed apnea index < 5 events /hour. Consent to study's timeline; willingness to wear home sleep test apparatus for at least 4 nights and to wear an oral appliance every night for 8 weeks; willingness to pick up and return home sleep test kits as needed.

d. Exclusion criteria

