Cardiac & pulmonary disease (e.g., congestive heart failure, severe arrhythmias, COPD); central sleep apnea; comorbidities of other sleep disorders other than OSA; no active TMD or jaw muscle pain, morphological airway abnormalities, BMI ≥35; pre-existing difficulty swallowing; throat or neck related health issues; endocrine dysfunction; severe psychiatric disorders; intellectually disabled; previous OA therapy; previous ENT surgery; restrictions in jaw opening; pregnant / breast feeding or intent to become pregnant during the study; inability to provide informed consent and apply the HST recorders.

e. Table 4: Variables of Interest: Primary, Secondary and Exploratory

Prima	ry	Secondary	Exploratory
with f of-tre secon treatn OA; T	art-of-treatment irst OA; T ₂ -end-atment with d OA; T ₃ -start-of-nent with first f ₄ -end-of-nent with second	T ₁₋₄ Snore count; OA compliance; Mean disease alleviation; Sleep Quality T _{0, 2, 4} Epworth Sleepiness Scale score; Short Form-36 score Thornton snoring scale Sleep observer scale Symptom alleviation Changes in occlusion as measured by shim stock, tested before and after	T ₄ OA device preference and perceptions of comfort; Development of a cost effective titration protocol with maximal patient convenience.

Mean disease alleviation is a composite measure of the reduction in RDI and OA compliance. RDI, respiratory disturbance index equals the number of respiratory events per hour of recorded time; $T_{1,4}$, time points 1-4

- f. Data collection techniques to be used during sleep
 - 1. OA compliance
 - i. This variable is determined by the number of hours that the OA device is worn per hour of sleep per night using Braebon monitors (integrated chips; Kanata, Ontario, Canada)
 - 2. Respiratory measures (Figure 3)
 - Braebon polygraphy (PG) recorder for home sleep testing: airflow, respiratory effort, electrocardiogram (ECG), pulse oximetry, anterior tibialis electromyography, body position, and snore sound.

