The rights, safety, and well-being of the study's subjects are the most important considerations and will prevail over the interests of science and society. The available non-clinical and clinical information associated with the investigational OAs is adequate to support the proposed clinical trial. The clinical trial is scientifically sound and has been described in a clear, detailed protocol herein.

The trial will be conducted in compliance with the protocol that has received prior Institutional Review Board (IRB) approval.

The care given to and decisions made on behalf of, subjects will be the responsibility of a qualified dentist and each individual involved in conducting the trial will be qualified by education, training, and experience to perform his or her respective task(s).

Freely given informed consent will be obtained from every subject prior to clinical trial participation. All clinical trial information will be recorded, handled and stored in a way that allows its accurate reporting interpretation and verification.

The confidentiality of records that could identify subjects will be protected, respecting the privacy and confidentiality rules in accordance with the applicable regulatory requirements.

IX.Schedule

The study duration will be approximately nine months. Each subject from the time of initial OA use and sleep data recording will be involved in the study for approximately 9 weeks. (Figure 6)

a. Recruitment criteria & methods: Potential study participants will be recruited from the Texas A&M College of Dentistry (TAMCD), local A.W.A.K.E. group. Invitation to participate in the study will be by bulk email and posted flyers. The study will be registered with ClinicalTrials.gov. Data analyst and subjects will be blinded to treatment device type (i.e. sequence of use of the two OAs) and subject's identity will be coded.

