b. After meeting the study's inclusion and exclusion criteria through telephone screening, study subjects will receive detailed information about the study from the Study Coordinator during their first appointment. The first appointment to the study center will include obtaining a copy of the patient's PSG/CPAP study reports and medical history, completion of the study's intake assessment, signing the informed consent form and obtaining impressions and protrusive bite. In the absence of a current PSG, subjects will be sent home with a HST to collect comparable baseline information. Both oral appliances will be constructed prior to the second appointment. The subjects will be randomized to an OA device at second appointment (this will allow any questions by the lab of the dentist to improve the device). During the second appointment, subjects will be examined and fitted by the dentist with both OAs. Subjects will be then scheduled within 4-weeks for the first HST with simultaneous SI recording for determination of the RDI and sleep quality criteria. Recordings will occur x1/subject at T₁ (first night in week-1 with first OA), T₂ (after four weeks using first OA), a washout period of 1 week using a mandible repositioner daily and CPAP nightly, T₃ (first night of week-6 with second OA) and T₄ (after four weeks using second OA). (Figure 1, below; Table 1)

c. Table 5: Protocol for determining subject candidacy:

EVALUATION	PURPOSE	PROCEDURE/RATIONALE
Recruitment / Orientation	Provide information about the study.	Provide the subject with information regarding the OA devices, the clinical study and an information brochure.
Medical Background Information	Gather information regarding the subject's medical background to determine candidacy, and recent sleep study evaluations.	Standard medical case history and physical with emphasis on OSA to include the Medical/Surgical History as part of the Case Report. Conducted individually by the team/Study Coordinator and discussed collectively to ensure that the subject has realistic expectations for the study.
Craniofacial & Oral Testing	Verify subject qualification with a craniofacial / oral exam.	Clinical assessment is performed to examine the upper airway and oropharynx to determine the subject qualification for using OA therapy.
Informed Consent	Obtain informed consent.	Informed consent will be obtained by providing information related to the time commitments of the trial, risks and contraindications.

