mastication are sufficiently healthy and stable for the safe participation in the study. If determined to be sufficient, the subject will then be fully enrolled in the study and have the study and tasks explained in greater detail. Dental impressions will then be obtained to prepare models for the fabrication of the custom oral appliances. Protrusive bite registrations will also be made at this time. Both oral appliances (OAs) will be constructed prior to the second appointment. During the second appointment, subjects will be examined and fitted by one of the study dentists with both OAs; if modifications are needed to improve fit, an OA may be sent back to the lab. The subjects will be assigned to one OA or the other at this second appointment according to predetermined randomization scheme. Neither the dentist nor the subject will know the assignment until the actual delivery. Subjects will be then scheduled within 4-weeks for the first home sleep study (HST, Medibyte system) with simultaneous SleepImage (SI) recording for determination of the Relative Disease Index (RDI) and sleep quality criteria. Recordings will occur x1 /subject at T_1 (first night in week-1 with first OA), T_2 (after four weeks using first OA), a washout period of 1 week using a mandible repositioner daily and CPAP nightly, T_3 (first night of week-6 with second OA) and T_4 (after four weeks using second OA) (Figure 1; Table 1).

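### Subjects are described as blinded to device type, but the design gives allocation concealment until delivery and a blinded analyst; the patient-reported outcomes are open-label

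*Combined protocol and SAP*

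**What the plan says.** Section VII.b (Population), item 2, says: "Data analyst and subjects will be blinded to treatment device type". A bracket after these words explains device type as the order of use of the two appliances. Section IX.a repeats the sentence. Item 3 of VII.b separately promises concealed allocation for the operators, so the plan uses both ideas and gives subjects the stronger one.

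Section 13.6 describes the second appointment. There, "subjects will be examined and fitted by one of the study dentists with both OAs", and assignment follows a predetermined scheme at the same visit: "Neither the dentist nor the subject will know the assignment until the actual delivery".

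Section II.b describes two adjustment mechanisms. The midline traction (MT) device has a single midline coupling that the patient advances in steps. For the bilateral thrust (BT) device, "The patient can modify the amount of protrusion by adjusting the mechanism on each of the two sides". Table 4 lists Epworth, SF-36, the Thornton snoring scale and symptom alleviation as secondary outcomes, and "OA device preference and perceptions of comfort" as exploratory at T4.

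**The concern.** A statement that subjects are blinded tells the reader that expectation about a device cannot explain a difference in what subjects report. Here the statement conflicts with the plan's own account of delivery and use.

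The matter is sharper than usual for two reasons. The alternative hypothesis in section V is directional in favour of MT, and the maker of the MT device (VII.g) is a named sponsor of the trial. A reader assessing the questionnaire results would want to know whether subjects could tell the devices apart. Study Limitations mentions the lack of a placebo device, the short acclimation and washout periods, scoring variability and recording conditions. It does not mention that subjects are unblinded, so nothing elsewhere in the plan corrects the sentence.

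**Working it through.** No arithmetic applies: the point changes no sample size, power or alpha. The check is whether a subject could be unaware of the device, or of the order of devices, when outcomes are measured.

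1. **Before allocation.** Table 5 has the coordinator do the following at orientation: "Provide the subject with information regarding the OA devices, the clinical study and an information brochure". Section 20.8 has the two arms explained at consent from a script. Subjects therefore know that two designs are being compared.

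2. **At the second appointment (13.6, IX.b).** Both appliances are fitted, so the subject has had each in the mouth before using either at home.

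3. **At delivery (13.6).** Concealment from subject and dentist lasts only until this moment, by the plan's own wording.

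4. **During each four-week period.**
   - The device comparison table before section V separates the designs by form and action: one contact point and a pull for MT, two contact points and a push for BT.
   - Section 13.6 has subjects put the appliance in and take it out themselves every night.
   - Sections II.b and VII.g (Appliance Acclimation) have the patient adjust each device, by different mechanisms, while awake.
   - VII.g has subjects log the settings in a diary.
   - No sham, matched exterior or other masking step appears anywhere.

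5. **When outcomes are collected.** T1 is the first night with the first device, so T1 to T4 all follow delivery. VII.f item 3 places Epworth, SF-36 and the Thornton scale at T0, T2 and T4. Only T0 precedes delivery; T2 and T4, the comparative measurements, come from subjects who know the device.

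6. **Does the gloss about order rescue the sentence?** No. With two devices and two periods, recognising the first fixes the second, so a subject who knows the device knows the whole sequence.

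The two accounts cannot both hold. Steps 2 to 4 support concealed allocation up to delivery. Section 17.2, which codes group assignment for the analyst, supports a blinded analyst. Nothing supports subject blinding after delivery.

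One side issue came up. The comparison table says a dental sleep specialist performs advancements for both devices, while II.b and VII.g have the patient adjust. Those passages must be reconciled. The conclusion does not depend on the outcome, because the subject handles the device every night either way.

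**The case against.** The best reply is that this is one loose sentence, repeated once, and that the rest of the plan already describes the true position: concealment for operators, assignment unknown until delivery, coded group for the analyst. Read together, those passages come close to the correction proposed here. That is fair, and no change of design is needed. But the sentence still makes a positive claim about subjects that section 13.6 contradicts.

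The plan also has features that limit expectation effects. People with previous appliance therapy are excluded, the consent script aims at equipoise, and presentation, fitting, monitoring and adjustment are to be the same for both devices. These deserve credit, but none hides the device from its user. The blinding tick-boxes in section 21.1 cannot be read in the available text, so nothing is inferred from them. Whichever was ticked, the sentence in VII.b and IX.a would still conflict with 13.6.

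Several stronger readings are tempting and are not supported:

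- **That the preference question, or keeping the devices, proves unblinding.** Preference could be asked of masked subjects as first versus second, and the devices become the subject's to keep only on completion.
- **That nightly wear is a self-report.** It is logged by a chip in the appliance. Knowing the device may change wearing behaviour, but that is not reporting bias.
- **That the primary result is compromised.** RDI is instrument-recorded and manually scored. Knowledge of the device can reach it only indirectly, through how far the patient advances the device and how much it is worn.
- **That the plan intends to claim superiority from questionnaires alone.** No passage says so; the hypotheses concern RDI.

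**Conclusion.** The sentence in VII.b and IX.a is wrong as written. The trial conceals allocation until delivery and blinds the analyst; from delivery onward, subjects and treating dentists know the device.

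This applies to every subject who receives an appliance (up to the planned 44) and to all patient-reported outcomes collected on treatment: Epworth, SF-36, Thornton snoring scale, symptom alleviation, preference and comfort. The direction and size of any bias cannot be worked out from the documents, and none is asserted. The conclusion assumes only that a subject who has been fitted with both appliances, and who handles one nightly, can tell one midline contact from two lateral ones.

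A reader might go on to infer that the analyst is unblinded or that the RDI comparison is invalid. Neither follows: analyst coding is stated and feasible, and RDI has only the indirect exposure described above. The consequence is confined mainly to what the subjective secondary and exploratory results can be said to show. The correction should be made, though it calls for no redesign.

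**What to change.** 1. In sections VII.b item 2 and IX.a, replace the sentence with: *Allocation is concealed until delivery; subjects and treating dentists are not blinded to device thereafter; the data analyst is blinded.*
2. Add the lack of subject blinding to Study Limitations, noting that RDI could be affected indirectly through patient-driven titration and wear.
3. State in the analysis section that Epworth, SF-36, the Thornton snoring scale, symptom alleviation, preference and comfort will be reported and interpreted as open-label.

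The cost is a few sentences. Procedures, data collection, sample size and the planned tests do not change. The downside is a weaker stated claim for the subjective secondary outcomes.

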During the approximately 2-hour Visit 1, the prospective subject will be given an oral exam by one of the team dentists to insure that the dentition, periodontium, temporomandibular joints, muscles of mastication are sufficiently healthy and stable for the safe participation in the study. If determined to be sufficient, the subject will then be fully enrolled in the study and have the study and tasks explained in greater detail. Dental impressions will then be obtained as models for the fabrication of the custom oral appliances.

k. Potential risk to subjects

The minor physical risk associated with the sleep-monitoring aspects of this study are no more than those involved with standards test of bodily (physiological) functions, for example wearing a heart monitor. The oral appliances are FDA cleared and are in wide use by dental patients throughout the US. The oral appliances (OAs) are FDA cleared and are in wide use by dental patients throughout the US. The OAs may cause pain in the jaw joint and teeth, and difficulty in opening or closing the jaw; these conditions are usually temporary. In the long term, the OAs may cause changes in tooth position and in the bite (occlusion), as well as damage to the teeth and gums. What makes this experience "research" rather than "routine clinical care" is that (1) the participants are randomly assigned to one OA or the other during the two active phases of the study, and (2) additional physiological measurements will be made beyond what are typically gathered during standard clinical practice. All of these tests are noninvasive.

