13.4 Inclusion/Exclusion Criteria	
What are the inclusion and exclusion criteria for study participation?	
Inclusion Criteria OSA diagnosed adults, at least 18 years old, who have been recently diagnosed by polysomnography (PSG) or polygraphy home sleep test (HST) in the previous year and are currently being treated with continuous positive airway pressure (CPAP) having an AHI > 15 events/hour of sleep; two or more OSA symptoms (snoring, witnessed apnea or daytime hypersomnolence complaint); at least 8 teeth per arch to support either OA device; Mallampati score from I to III; Palatine tonsils − grade 0, 1, or 2; Central and mixed apnea index < 5 events/hour. Consent to study's timeline; willingness to wear home sleep test apparatus for at least 4 nights and to wear an oral appliance every night for 8 weeks; willingness to pick up and return home sleep test kits as needed. Exclusion Criteria Cardiac & pulmonary disease (e.g., congestive heart failure, severe arrhythmias, COPD); central sleep apnea; comorbidities of other sleep disorders other than OSA; no active TMD or jaw muscle pain, morphological airway abnormalities, BMI ≥35; pre-existing difficulty swallowing; throat or neck related health issues; endocrine dysfunction; severe psychiatric disorders; intellectually disabled; previous OA therapy; previous ENT surgery such as uvulopalatopharyngoplasty; restrictions in jaw opening; pregnant / breast feeding or intent to become pregnant during the study; inability to provide informed consent and apply the HST recorders. Do the exclusion criteria exclude specific populations or individuals based on gender, culture, language,	
economics, race, or ethnicity? O Yes No	
If Yes, then justify each exclusion:	
In rest, their justify each exclusion.	
13.5 Describe the setting where the informed consent process will take place (e.g. classroom, clinic, laboratory, office, park, personal computer, etc.).	
If a waiver of documentation of informed consent is requested, then describe how participants will review the information sheet.	
College of Dentistry clinic.	

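### The exclusion list states the TMD item in the negative, so read literally it turns away subjects without active TMD or jaw pain and conflicts with the Visit 1 exam

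*Combined protocol and SAP*

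**What the plan says.** Section VII of the protocol, embedded in section 12.1 of the application, opens its list of disqualifying conditions with the heading "d. Exclusion criteria". Within that list stands the entry "no active TMD or jaw muscle pain", in the run "comorbidities of other sleep disorders other than OSA; no active TMD or jaw muscle pain, morphological airway abnormalities", followed after a comma by the BMI limit. Section 13.4 of the application repeats the item under its own exclusion heading: "no active TMD or jaw muscle pain, morphological airway abnormalities".

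Section VII.j describes a dental exam at Visit 1. The dentist is to confirm that the teeth, the supporting tissues and the "temporomandibular joints, muscles of mastication are sufficiently healthy and stable for the safe participation in the study". The consequence follows directly: "If determined to be sufficient, the subject will then be fully enrolled in the study". Section 13.6 describes the same exam and the same consequence.

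Section IX.b says the inclusion and exclusion criteria are met by telephone screening before the first appointment. Section 13.6 allows direct or telephone screening. Both put screening before the exam, and both put assignment to an appliance at the second appointment.

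**The concern.** An exclusion list works in one direction: a subject who meets an entry is out. An entry that describes the absence of a problem reverses that direction. Here the reversed entry concerns the jaw joint and jaw muscles, which the oral appliances load and in which the risk section (VII.k) expects some pain or reduced function.

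This is operative text. It is the only entry in either list that names TMD or jaw muscle pain, and the lists are what screening staff apply before any dentist sees the subject. If the written rule and the exam point in opposite directions, no subject can satisfy both cleanly, and the trial's record of who was eligible rests on staff reading past the wording.

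**Working it through.** No arithmetic applies. The check sets the texts side by side.

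**1. Direction of the list.** The other entries in VII.d and 13.4 name a condition whose presence excludes: heart and lung disease, central sleep apnea, earlier appliance therapy and, for example, "restrictions in jaw opening; pregnant / breast feeding or intent to become pregnant during the study". The TMD entry is the only one phrased as an absence.

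**2. Applying each rule to two subjects.**

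| Subject | Exclusion item read literally (VII.d, 13.4) | Visit 1 exam (VII.j, 13.6) |
|---|---|---|
| No active TMD or jaw pain; joints and muscles healthy and stable | Meets the item, so excluded | Jaw requirement met; may be fully enrolled |
| Active TMD or jaw pain | Does not meet the item, so not excluded by it | Enrolled only if the dentist still finds joints and muscles sufficient |

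In the first row the rules contradict each other outright. In the second row the exclusion item is silent and the exam decides.

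**3. Order of steps.** Screening against the lists comes first, then the exam at the first appointment, then impressions and appliance construction, then fitting and random assignment at the second appointment. The exam can therefore stop a subject with active TMD before randomization. It cannot see anyone already turned away at screening.

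**4. Artefact or copying slip?** The wording of this item is the same in both lists. The lists are not pure copies of each other, because 13.4 adds an example of ENT surgery that VII.d lacks. Nothing elsewhere in the documents corrects or explains the item.

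**5. Reach of the negative.** Semicolons separate most entries, but commas join the TMD item to the airway-abnormality entry and the BMI limit. It is unclear on the page whether the negative governs only TMD and jaw pain or also what follows.

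**6. Consequence for deviations.** If the exam works as described, enrolled subjects have sufficiently healthy jaws. Under the literal item, each enrolled subject without active TMD or jaw pain is an eligibility deviation, potentially all of the 44 to be recruited. Section 26.1 (item 4) requires protocol deviations to be reported to the IRB immediately.

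**The case against.** The best defence is that nobody will be misled. The intended meaning can be inferred from the rest of the list, from the exam text and from the risk section. A literal reading would leave the trial with almost no one to enrol, so the slip would surface at the first screening call. The protocol's real check on the jaw is the hands-on exam, which the slip does not touch. Table 5 adds a craniofacial and oral exam to verify qualification, and restricted jaw opening is a separate exclusion.

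Much of this stands. A reader might infer that the plan admits subjects with active TMD. The documents do not support that: failing to meet one exclusion item admits nobody, and the Visit 1 exam precedes randomization. A reader might also infer that recorded eligibility data will be uninterpretable, or that RDI, compliance and drop-out will be distorted by TMD patients in the sample. No screening form for this item is in the documents, no text or figure links existing TMD to those outcomes, and the inference needs such patients to pass the exam.

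What the defence does not answer is that the written rule is still wrong, in two places, and is applied before the exam. Staff reading it as intended are departing from the approved text.

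**Conclusion.** The point holds as a wording defect in an operative eligibility rule. Read as an exclusion, the item shuts out subjects without active TMD or jaw pain, does not itself shut out those with it, and contradicts the Visit 1 exam in VII.j and 13.6. The practical exposure is limited to two things: eligible people who could be wrongly turned away at screening, and enrolled subjects who are deviations on the literal text. How many of the former there would be cannot be estimated from the documents and depends on whether staff follow the words or the evident intent, which is probably the latter.

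The power calculation, the 38 completers and 44 recruits, the crossover comparison and the planned tests are unaffected. The conclusion assumes only that the exclusion heading means what it says and that the lists are applied as section IX.b describes. The correction should be made because the rule is wrong as written and costs almost nothing to put right.

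**What to change.** Reconcile the direction of this item in VII.d and 13.4 with the Visit 1 exam text in VII.j and 13.6, so that screening and exam point the same way. This can be done by wording the entry like its neighbours, as a condition whose presence excludes, or by moving the phrase as it stands to the inclusion list; the two give the same rule. Set it off from the airway-abnormality and BMI entries with semicolons so that the reach of the negative is plain. Check that any telephone or in-person screening checklist carries the same wording; none is among the documents, so whether it needs changing is unknown.

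The cost is a few words in two sections, submitted as a minor amendment to the IRB. No procedure, sample size or analysis has to change.
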